3.2 Number of Subjects

560 subjects divided into two arms.

3.3 Duration of Participation

Subjects will participate in the study for 30 days following discharge from the hospital or until the chest tube has been removed if it remains in place more than 30 days post hospital discharge.

3.4 Primary Study Endpoints

Reduction in empyema in patient's discharging with an indwelling chest tube and valve.

3.5 Secondary Study Endpoints

Reduction of 30-day readmission in patient's discharging with an indwelling chest tube and valve.

3.6 Identification of Source Data

The following source data will be directly recorded on the Case Report Form (CRF):

• Patient Chest Tube Diary

The following source data will not be directly collected in the Case Report Form (CRF), but will be captured in supportive documentation (study source documents, electronic medical record):

- Laboratory results and clinical interpretation of the values
- Clinical significance of observations
- Hospital admissions

4 Subject Selection Enrollment and Withdrawal

4.1 Inclusion Criteria

- ≥ 18 years of age
- Male or Female
- Consultation with a thoracic surgeon
- Discharge from the hospital with a chest tube and valve in place
- Subject is able to understand the study procedures and provide informed consent.

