1.2 Clinical Data to Date

Several studies report prolonged air leak rates in the 10-15% range following lobectomy (1-3). Prolonged air leak has been shown to be a primary driver in prolonged length of stay and increased hospital costs (6-9). Varela and colleagues found air leaks longer than 5 days increased rate of pulmonary complications including atelectasis, pneumonia, or empyema (7). Brunelli and colleagues reported an increased rate of empyema of 8.2% to 10.4% in patients with prolonged air leaks lasting more than 7 days versus only 0% to 1.1% in patients with shorter air leaks (14). This study also showed that longer air leaks led to further interventions; however, this was not in patients discharged from the hospital (14).

Dismissal from the hospital with a chest tube in place is not a novel concept. Multiple groups have advocated for this practice. McKenna and colleagues reported on fast-tracking thoracoscopic patients. They utilized this strategy in 2.5% of patients (7/282) and reported only one patient required readmission (12). Another study by Rieger et al. utilized the mini-Atrium[®] device for dismissal of patients with a chest tube in place for either effusions or air leak. They reported a rate of minor complications in 11% (4/36), which included 3 readmissions, one of which was for an empyema (13). Royer et al. described similar practice with dismissal of 65 patients with a chest tube and Heimlich

valve (13%, 65/496). Two patients were readmitted and 4 had superficial site infections requiring oral antibiotics but no empyema was reported. Overall they reported a potential savings of 305 inpatient hospital days (11). In light of these findings, hospital length of stay is decreased and, concurrently, cost with this practice. These studies encourage the practice with little complications.

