1.3 Risks and Benefits

All study interventions could be considered standard of care.

Cerfolio and colleagues cite the use of oral antibiotics while the chest drain is in place but they do not address any risks or benefits but state it is merely their preference (3). In the study conducted by Reinersman and colleagues, the 27 patients discharging with indwelling chest tubes in place that received prophylactic antibiotics at discharge were found to have no complications from the antibiotics (15). Cerfolio, Reinersman and colleagues have reported that an air leak lasting longer than 7 days leads to an increased risk of empyema (14, 15).

The Surgical Care Improvement Project (SCIP) Performance Measures endorse pprophylactic antibiotics discontinued within 24 hours after surgery end-time. There is no significant evidence showing a benefit to continuing antibiotic usage beyond 24 hours. Prolonged administration of antibiotic usage may increase the risk of drug resistance and secondary infections, such as *Clostridium difficile* (16).

2 Study Objectives

Primary Objective

To assess the efficacy of antibiotics and closer monitoring on decreasing empyema in patients discharging with a chest tube and valve in place as measured by documented empyema following discharge.

Secondary Objective

To assess the efficacy of antibiotics and closer monitoring on decreasing hospital readmissions while the chest tube and valve are in place as measured by readmission to the hospital following hospital discharge after the initial surgical intervention.

3 Study Design

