3.1 General Description

This study is a multicenter, randomized trial for the treatment of subjects discharging from the hospital with a chest tube and valve in place. Subjects will be screened prior to discharging from the hospital and interested qualified subjects will be consented and offered participation in this trial. Once consent has been obtained the subject will be randomized to receive oral antibiotics and close monitoring, defined as twice weekly telephone calls by a member of the care team, of their chest tube and valve or standard of care, defined as no calls from the care team but waiting for the subject to contact the care team when the air leak has stopped. The subject will be followed until they have their chest tube removed.

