4.4.2 Data Collection and Follow-up for Withdrawn Subjects

Information collected before the participant withdraws consent can continue to be used; however, new information will not be collected.

5 Study Procedures

5.1 Visit 1

The subject will be identified for eligibility into the study. The study coordinator will consent and enroll the subject. For women of childbearing potential, a pregnancy test will be done if not done prior to surgery and it must be negative before you can continue in this study. Baseline data collected will include air leak status and surgical history.

5.2 Visit 2

Prior to their discharge from the hospital a member of the study team will review the instructions for completing the Patient Chest Tube Diary and will confirm that the standard clinical education for discharging with an indwelling chest tube and valve has been completed. For subjects randomized to Group 1 confirm that they have received their prescription for antibiotics. The antibiotic to be prescribed is cephalexin; it is the oral equivalent of the antibiotic used for perioperative coverage. In the event that the subject has an allergy to cephalexin or the cephalosporin group of antibiotics then clindamycin should be prescribed instead in following the typical perioperative coverage.

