14.2 Twice Weekly Telephone Script

Twice Weekly Telephone Script

Protocol Title: A Randomized Study Evaluating Patients Discharged with Indwelling Chest Tube and Valve IRB #: 17-007774

Principal Investigator: [name]

Introduction:

Hello, this is _____ calling from the Mayo Clinic in Rochester, Minnesota (if out of state). May I please speak to _____?

***If the participant is there continue with the script.

***If the participant is not there, ask when it would be a good time to speak with ?

Describe the Reason for the Call:

We are calling to check in on the progress of your air leak and indwelling chest tube and valve. If you may recall you agreed to participate in A Randomized Study Evaluating Patients Discharged with Indwelling Chest Tube and Valve and you were randomized to the group which receives twice weekly telephone calls to follow up on your indwelling chest tube.

Does your indwelling chest tube with valve have an air leak?

- 🗆 No
- Yes

If yes, has the air leak changed?

🗆 No

Yes

If yes, please explain:

Is there anything else we need to know about your indwelling chest tube and valve?

Closing

Thank you for participating in our research study. Please understand that your answers will remain confidential. Give them some follow-up contact information (name and telephone number) in case they think of any more questions afterwards.

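### Eligibility requires neither an air leak nor an operation, yet the control contact trigger and call script assume a leak and the secondary objective assumes surgery; baseline leak status should be a stratification factor and a prespecified covariate

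*Protocol*

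**What the plan says.** **Who may enter.** Section 4.1 asks for age 18 or over, "Consultation with a thoracic surgeon", "Discharge from the hospital with a chest tube and valve in place", and capacity to consent. The exclusions in 4.2 concern pregnancy, allergy and conditions that antibiotics might worsen. Neither list mentions an air leak or an operation.

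**What the arms are.** Section 3.1 gives the intervention arm oral antibiotics and "close monitoring, defined as twice weekly telephone calls by a member of the care team". The control arm receives no calls; its care is "waiting for the subject to contact the care team when the air leak has stopped".

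**What the calls ask.** The script in 14.2 introduces the call as a check on how the leak is progressing. It then asks "Does your indwelling chest tube with valve have an air leak", with a No box; if the answer is yes, it asks whether the leak has changed. One open question about the tube and valve follows.

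**What is counted.** The secondary objective in section 2 is measured by "readmission to the hospital following hospital discharge after the initial surgical intervention". The secondary endpoint in 3.5 and the readmission hypothesis in 6.2 refer to neither surgery nor a leak.

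**What is recorded and used.** Section 5.1 says: "Baseline data collected will include air leak status and surgical history". Section 8.3 stratifies randomisation by enrolling site only. In section 6.2, covariates enter the logistic models if they turn out importantly imbalanced between the arms.

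**The concern.** Sections 1.1 and 1.2 build the case for the trial on prolonged air leak after thoracic surgery, but entry depends on the device a patient goes home with, not on why it was left in. The background shows that these differ: one cited series covered "dismissal of patients with a chest tube in place for either effusions or air leak". A patient with a drain for an effusion and no leak meets section 4.1.

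If such a patient is allocated to control, the event that should prompt contact cannot occur. If the patient is allocated to the intervention, the structured part of each call concerns something the patient does not have. Separately, an eligible patient who had no operation falls outside the literal wording of the secondary objective.

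Two things are at stake. The comparator should be defined for everyone who can be randomised. And leak status, which the background treats as a driver of empyema, is left to chance within site and reaches the model only if an imbalance is noticed.

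**Working it through.** **1. Set the sections side by side.**

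| Protocol section | Assumes a leak? | Assumes an operation? |
|---|---|---|
| 4.1 and 4.2, eligibility | No | No |
| 3.1, intervention calls | No, they are scheduled | No |
| 3.1, control contact trigger | Yes | No |
| 14.2, opening of the script | Yes | No |
| 14.2, leak question | No, it has a No box | No |
| 2, secondary objective | No | Yes |
| 3.5, secondary endpoint | No | No |

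The two conditions are separate. The control trigger and the script's opening assume a leak. The secondary objective assumes surgery.

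**2. Reproduce the planned sample size.** Section 6.1 gives a two-sided 0.05 test, 80% power, a 50% reduction and 253 per arm, but no control rate. I assume the 16.5% quoted in section 1.2, so 8.25% under treatment. With pooled variance under the null:

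n = [1.96·√(2·p̄·(1−p̄)) + 0.8416·√(p1(1−p1) + p2(1−p2))]² / (p1−p2)²

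With p1 = 0.165, p2 = 0.0825 and p̄ = 0.12375, this is (0.9127 + 0.3889)² / 0.006806 = 249 per arm, within 3% of 253. Power at 253 per arm is 80.6%. The sample size is not shown to be wrong.

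**3. Ask whether leak-free patients would cost power.** The protocol does not give their share, f. The table takes f = 10%, 20% and 30% with 253 per arm; every row is an assumption.

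| Assumption for leak-free patients | Rates compared | Power at f = 10% / 20% / 30% |
|---|---|---|
| Same risk, same 50% reduction | 16.5% v 8.25% | 80.6% / 80.6% / 80.6% |
| Same risk, half the reduction (25%) | 16.5% v (1−f)·8.25% + f·12.375% = 8.66% / 9.08% / 9.49% | 75.9% / 70.7% / 65.1% |
| Same risk, no effect | 16.5% v (1−f)·8.25% + f·16.5% = 9.08% / 9.90% / 10.73% | 70.7% / 59.3% / 47.4% |
| Control risk 1.1%, same 50% reduction | (1−f)·16.5% + f·1.1% = 14.96% / 13.42% / 11.88%, v half of each | 76.1% / 70.9% / 65.1% |

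The result runs from no loss to a large loss, and nothing in the protocol says which row applies.

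**4. Check that the extra covariate is affordable.** Under the planning rates, expected empyemas are 253 × 0.165 + 253 × 0.0825 = 41.7 + 20.9, or about 63. One binary covariate is a small demand on that number. A leak-free subgroup of 10% to 30% of 506 would be about 51 to 152 patients, so results by leak status would be descriptive.

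**The case against.** **The monitoring contrast survives.** A reader might infer that monitoring does not differ between the arms for leak-free patients. The protocol does not support that. Calls go to Group 1 twice a week whatever the leak status, and control patients get none. The schedule of events places adverse-event evaluation at these calls, section 7.2 requires specific questioning about adverse events at each contact, and the script closes with an open question. A call can therefore pick up a problem in a leak-free patient. This stands and limits the point.

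**Control patients are not without care.** Section 5.2 has the team confirm standard discharge education with no restriction by arm. At the centre described in 1.2, that education also covered dressings and changes in output. This stands too; what is missing is one trigger, not all care.

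**The population is stated consistently.** The summary, the primary objective, both endpoints and section 4.1 all name patients discharged with a tube and valve. Breadth may be deliberate, so narrowing entry to patients with a leak after surgery is not a correction the documents call for.

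**The power figures cannot be pressed.** The 16.5% is described as coming from patients discharged with an indwelling tube, not from a leak-only group; diluting it again may count the same patients twice. The 1.1% is the top of a range for shorter leaks in a study that section 1.2 says was not of discharged patients. Halving the effect assumes that the calls supply half the benefit and do nothing without a leak.

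**What the objections leave.** The No boxes in the script and diary also serve patients whose leak has stopped, and they give a never-leaking control patient no trigger. Adjusting only for an imbalance once seen makes the model depend on the data.

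**Conclusion.** The mismatch is real and limited. Eligibility requires neither a leak nor an operation, the control trigger and the script's opening assume a leak, and the secondary objective assumes surgery. For an eligible leak-free patient the control contact trigger is undefined and the script's structured questions have little to act on. The antibiotic contrast is unaffected, and calls and adverse-event questioning still separate the arms.

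No loss of power is established. A reader might take the lower figures in the table as the expected cost, but each rests on an assumed leak-free share and an assumed difference in effect or risk, and under equal risk and benefit power stays at 80.6%.

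The case for using leak status in the design needs none of those assumptions. The variable is already collected, and section 1.2 links longer leaks to empyema: 8.2% to 10.4% with leaks beyond 7 days against 0% to 1.1% with shorter ones. That contrast concerns leak duration in patients not discharged, so it supports leak as a plausible prognostic factor but does not size the gain. This is a cheap improvement, not a flaw that threatens the trial.

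**What to change.** Keep the stated population, and:

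1. Add baseline air leak (yes/no) as a stratification factor beside site in the randomisation module described in 8.3. Visit 1 already records leak status; it must be entered before allocation.
2. In 6.2, prespecify baseline leak as a covariate in the logistic and Cox models for 30-day empyema and 30-day readmission, whatever imbalance is observed.
3. Report both outcomes by baseline leak status, as description.
4. Reconcile the control definition in 3.1 and the secondary objective in section 2 with 4.1, so that each applies to every eligible patient. What the contact rule should be for a leak-free patient is a clinical decision for the investigators.

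The cost is a protocol amendment, one extra randomisation field and somewhat smaller strata, since each site's stratum splits in two. No patients are lost and no new data are collected.

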4.2 Exclusion Criteria

- Pregnancy
- Allergy to cephalexin or clindamycin
- Special consideration should be taken in enrolling subjects with preexisting conditions that can be exacerbated by antibiotic use but are allowed at the discretion of the treating physician.

Considerations include but are not limited to:

- C. difficile
- Colitis
- Impaired renal function
- Hypersensitivities to cephalosporins, penicillins, or lincomycin
- Hepatic impairment
- Anticoagulation therapy
- Metformin usage
- Probenecid usage

4.3 Subject Recruitment, Enrollment and Screening

A member of the research team will identify that a potential subject is going to be discharged from the hospital with a chest tube and valve in place. Once the subject's eligibility for the study has been determined the background of the proposed study and the benefits and risks of the study and procedures will be explained to the subject as a part of consenting process.

A signed, written informed consent document will be obtained from each subject by the investigator or his/her designee prior to the subject's involvement in the study. Routine clinical evaluations that would be performed as part of the normal clinical care of patients may be performed prior to such consent and used as part of the screening assessment. If the patient is subsequently consented and enrolled in the study, the results of such tests may be used as study data.

The process of obtaining informed consent will include the investigator or investigator's designee informing all subjects about:

- The expected duration and purpose of the study.
- The method of application and investigational nature of the device.

- The potential risks and benefits that may result from utilization of the device.
- The right to refuse participation in this clinical investigation and that if they should choose to participate, they may withdraw from the study at any time.

After consenting, subjects will be considered enrolled if they meet all the inclusion criteria and none of the exclusion criteria. Subjects who fail to meet any of the entry criteria will be excluded from the study and considered a screen failure. Screen failures will be recorded, and the reason(s) for exclusion will be documented.

4.4 Early Withdrawal of Subjects

4.4.1 When and How to Withdraw Subjects

Subjects may withdraw from the study at any time. Additionally, a subject may also be discontinued from the study, if, based on the judgment of the Investigator, it is in the best medical interests of the subject. Withdrawal initiated by the patient may be documented by written or oral withdrawal of the original informed consent, or the implicit withdrawal of consent reflected in patient noncompliance or the patient being lost to follow-up.

Subjects are considered "lost to follow-up" after 3 attempts to contact the participant. Study coordinators will document all attempts to contact subjects.

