5.4 Twice Weekly Telephone Calls (Group 1 Only)

The subjects in Group 1 will receive twice a week telephone calls from their coordinating medical team. Attachment 14.2.

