6.3 Subject Population(s) for Analysis

The primary analysis will be intention to treat (ITT). A secondary analysis will be considered using a per protocol (PP) analysis.

7 Safety and Adverse Events

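### Sections 4.4.1 and 4.4.2 allow nonadherence or three contact attempts to end outcome collection as implied withdrawal of consent, which conflicts with the ITT analysis and bears more on Group 1

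*Protocol*

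**What the plan says.** Section 4.4.1 lists how withdrawal by the patient may be documented. Besides written or oral withdrawal of consent, it accepts "the implicit withdrawal of consent reflected in patient noncompliance or the patient being lost to follow-up". A subject is lost to follow-up "after 3 attempts to contact the participant"; no spacing, time window or anchor date is given, and noncompliance is not defined.

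Section 4.4.2 gives the consequence: "Information collected before the participant withdraws consent can continue to be used; however, new information will not be collected". The only provision for later information is in section 8.1. It concerns subjects who revoke authorization to use health information, and it asks for permission to collect at least vital status, which is neither study endpoint.

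The arms differ in what a patient can fail to do. Section 5.4 reads "The subjects in Group 1 will receive twice a week telephone calls from their coordinating medical team", and section 5.2 gives the antibiotic to Group 1 only. In section 3.1 the control arm is "defined as no calls from the care team but waiting for the subject to contact the care team when the air leak has stopped". Both groups keep the daily diary (5.3, 14.1), and a diary-return call may be made to either (5.5, 14.3).

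Sections 6.2 and 6.3 make the primary analysis ITT, with per protocol secondary. Section 6.2 foresees differential censoring and turns to Kaplan-Meier and Cox methods if 30-day follow-up is incomplete.

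**The concern.** An ITT analysis needs the outcome of every randomized patient, whether or not the patient took the drug, answered the telephone or filled in the diary. Sections 4.4.1 and 4.4.2 together allow the outcome to be lost for exactly those reasons. Drug and calls are also the intervention under test, so loss by this route is tied to the treatment arm.

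At stake is the primary comparison. If the patients who drop out of observation differ in empyema risk from those who stay, and more drop out of one arm, the arms are no longer comparable as randomized. A later analysis plan cannot recover outcomes that the protocol stopped collecting. Much of the loss is avoidable: section 3.6 already takes hospital admissions and laboratory results from source documents and the electronic medical record.

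**Working it through.** **1. The plan's own figures.** Section 6.1 states 253 per arm (506 in total) for a 50% reduction in empyema, two-sided 0.05, 80% power, and 560 after an additional 10% for dropouts. It names no control rate. Taking 16.5% from the earlier cohort in section 1.2 (an assumption), with p1 = 0.165, p2 = 0.0825 and mean 0.12375:

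n = [1.96 × √(2 × 0.12375 × 0.87625) + 0.8416 × √(0.165 × 0.835 + 0.0825 × 0.9175)]² / 0.0825² ≈ 249 per arm.

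This is close to 253, and 506 × 1.10 = 557 or 506 / 0.90 = 562 is close to 560. The sample size is not in dispute. The loss allowance is 560 − 506 = 54 patients and is not split by arm. Divided equally it is 27/280 = 9.6% per arm; if all of it fell in Group 1 it would be 54/280 = 19.3%.

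**2. Exposure to the rule, by arm.**

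| Way to be noncompliant or unreachable | Group 1 | Group 2 |
|---|---|---|
| Antibiotic not taken (5.2, 14.1) | yes | not applicable |
| Scheduled twice-weekly call missed (5.4) | yes | not applicable |
| Diary not kept (5.3, 14.1) | yes | yes |
| Optional diary-return call missed (5.5, 14.3) | yes | yes |

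Exposure is greater in Group 1 but not confined to it.

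**3. Effect on the estimate.** Assume no treatment effect, 16.5% true risk in both arms and no loss in Group 2. A fraction f of Group 1 is removed before any event and has k times the risk of those who stay. Then:

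observed Group 1 risk = 0.165 / [(1 − f) + f × k]; RR = 1 / [(1 − f) + f × k].

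| f | k | Denominator | Observed Group 1 risk | RR |
|---|---|---|---|---|
| any | 1 | 1.00 | 16.5% | 1.00 |
| 10% | 1.5 | 0.90 + 0.15 = 1.05 | 15.7% | 0.95 |
| 15% | 2 | 0.85 + 0.30 = 1.15 | 14.3% | 0.87 |
| 20% | 2 | 0.80 + 0.40 = 1.20 | 13.75% | 0.83 |
| 20% | 0.5 | 0.80 + 0.10 = 0.90 | 18.3% | 1.11 |

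The last row shows that the sign reverses if the lost patients are at lower risk. All values of f and k are assumed.

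**4. Effect on the test.** Under the same null, but now with 5% of Group 2 lost at random, n1 = 280 × (1 − f) and n2 = 280 × 0.95 = 266. Let d = 0.165 − observed Group 1 risk, se0 the pooled and se1 the unpooled standard error. The two-sided false-positive rate is

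Φ[(d − 1.96 se0)/se1] + Φ[(−d − 1.96 se0)/se1].

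For f = 20%, k = 2: n1 = 224, d = 0.0275, se0 = 0.0326, se1 = 0.0324, giving 0.130 + 0.002 ≈ 13%. For f = 10%, k = 1.5 it is 5.7%; for f = 15%, k = 2 it is 10%; for k = 1 it stays at 5%.

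**5. The fallback.** Kaplan-Meier and Cox methods use follow-up up to withdrawal, so the shift would usually be smaller than in step 3, where patients are removed from the start. They still treat a censored patient as having the same future risk as those remaining in that arm. If k differs from 1 after censoring, that condition fails.

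**The case against.** Several points on the other side are sound and limit the concern.

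- **The rule is permissive.** Section 4.4.1 says how withdrawal may be documented; it does not oblige a site to treat a missed dose as withdrawal. Other text points away from that reading: the Group 1 diary records days without antibiotic as data, section 6.3 foresees a per-protocol analysis, and section 7.2 follows adverse events to resolution. A reader might infer that Group 1 becomes a complier-only sample and that ITT fails outright; the documents do not support that. What remains is that sites may apply the wording differently, and nothing in 4.4 protects the outcome of a patient once classed as withdrawn.
- **Unanswered calls.** A reader might infer that three missed scheduled calls, about ten days at two a week, make a Group 1 patient lost to follow-up. No section equates a scheduled care call with a contact attempt under 4.4.1. The protocol does not rule it out either, so the definition needs to be explicit.
- **Direction.** It is tempting to say that the bias favors the intervention, because patients who stop antibiotics or fall silent may be sicker. A patient whose tube came out early also has less reason to answer, and section 1.2 links shorter tube duration to lower empyema risk. Either sign is possible.
- **Already foreseen.** Section 6.2 anticipates differential censoring and section 6.1 allows for dropout. That covers the loss of numbers. It does not cover loss related to risk, and sensitivity analyses in a separate analysis plan would have to rest on assumptions in place of the missing outcomes.
- **Records alone may not suffice.** Section 3.6 does not say that the endpoints need no patient contact, and admissions elsewhere may come to light only through contact.

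**Conclusion.** The concern holds as a conflict in the text with a built-in risk of bias. Sections 4.4.1 and 4.4.2 permit outcome collection to stop for nonadherence or failed contact, sections 6.2 and 6.3 need that outcome, and Group 1 has more ways to meet the rule. Whether the results would be biased depends on two things that the protocol does not give: that loss differs between arms, and that it is related to empyema risk.

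The size is therefore only illustrative. With 16.5% risk in both arms and loss in Group 1 alone, the null risk ratio moves from 1.00 to 0.95 or 0.83 in the two main scenarios, not at all if risk is equal, and the other way if lost patients are at lower risk. The 20% scenario roughly equals the plan's whole dropout allowance falling in Group 1, so it is an upper anchor and not a forecast.

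**What to change.** **Section 4.4.1.** State that noncompliance with study treatment, calls or diary, and unanswered calls, are not withdrawal of consent. Give one lost-to-follow-up definition, with a time window, that applies identically in both arms and does not count missed Group 1 intervention calls. It should not hang on a day-30 contact, because the protocol schedules none (section 5.5 has only an optional diary reminder); adding one would mean adding it in both arms.

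**Section 4.4.2.** State that 30-day empyema and readmission continue to be collected from the medical record for all randomized patients unless the patient explicitly withdraws consent for this.

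**Cost.** Amendment wording, possibly one consent-form sentence, and a little more record review. No extra patients are needed: at 16.5% against 8.25%, power is 80.6% with 253 per arm and would be 84.4% if the outcome were known for all 280 per arm. The limit is that events treated outside the site may still be missed.
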